6.5.2 Timing and Method of Informed Consent

Investigator provides sufficient explanation to before conducting the study, using the consent form and other written information for patients, confirms that the participants fully understood the explanation, and then obtains written voluntary consent of the participants themselves to the participation in the study. Investigator who provided the

explanation and the subject write down their names and place their seals on or sign and date the consent form.

Investigator gives a copy of the consent form and other written information for patients to the participants who agreed to participate in the study and records it. The above receipt of documents can be recorded in a column for receipt prepared in the medical record or the consent form. The original consent form is retained at the designated area at each study site.

Investigator enters the date of consent in the case report form.

6.5.3 Points for Consideration in Acquisition of Consent

The principal investigator, sub-investigator, or clinical research coordinator shall consider the following points regarding acquisition of consent.

- Participants must be neither forced to participate or continue to participate in the study nor unduly influenced in their decisions.
- In the explanation, any phrases that make or appear to make participants waive their rights or release or appear to release the principal investigator, sub-investigator, CRC, study site, and sponsor from liability must not be used.
- In the explanation, words that are understandable to participants and as non-technical as possible must be used.
- Before consent, participants must be given a chance to ask questions and sufficient time to decide whether to participate in the study. On the above occasion, all the questions must be answered to the satisfaction of the participants.

6.5.4 Revision of Consent Form and Other Written Explanation for Patients (provision of new information)

- (1) When Investigator obtained new information that may influence the intention of participants to continue to participate in the study or may be related to the consent of the participants (including reports of serious ADRs), Investigator verbally gives the information concerned to the participants immediately and confirms whether or not the participants intend to continue to participate in the study. Investigator also records the information Investigator has given and the result of confirmation in the medical record or other documents.
- (2) In cases described in (1), if the principal investigator acknowledges the necessity of revision of the consent form and other written information for patients, principal investigator promptly revises the consent form and other written information for patients based on the information concerned and newly obtains the approval of the institutional review board.
- (3) Investigator provides explanation again using the consent form and other written information for patients that were revised according to the rule in (2) to the participants including those who already received the information concerned verbally and obtains their written consent to continuation of participation in the study. However, explanation does not have to be provided to the participants who already completed the study.

6.6 Subject Enrollment

A unique subject IDs will be assigned to each participant by the Investigator at 1st visit. This number will serve as the participant's identifier in the study as well in the study database. This subject IDs will be unique across each site and it will be a 5 digit number including last three digits will be the subject ID at each site with hyphen between the site number and the last three digits. Site number will be assigned by Sponsor.

At the start of the study, the principal investigator assigns participant ID to the participants who gave written consent by themselves. Two copies of the screening list of participants that includes the information of the participants who gave consent are prepared. One copy is retained and the other copy is submitted to the sponsor. Regarding the participants who were not enrolled, the reason is recorded.

On the CRFs or other documents submitted to the Sponsor, participants should not be identified by their names, but by their assigned subject IDs only. If subject names are included on copies of documents submitted to the Sponsor, the names must be obliterated and the assigned subject ID added to each of the documents.

6.7 Sample Size

Assumptions

- Outcome	: Pain score
- Standard deviation (σ)	: 1.81
- Clinically meaningful margin (Δ or δ)	: 1.0
- Power	: 80% ($Z_{1-\beta} = 0.84$)
- Significance level (α)	: 0.05

Reference standard deviation from Kocak AO, Dogruyol S, Akbas I, Menekse TS, Gur STA, Kocak MB, Cekmen B, Orun S, Cakir Z. Comparison of topical capsaicin and topical piroxicam in the treatment of acute trauma-induced pain: A randomized double-blind trial. Am J Emerg Med. 2020 Sep;38(9):1767-1771. doi: 10.1016/j.ajem.2020.05.104. Epub 2020 Jun 2. PMID: 32739846.

For **equivalence trials with 3 groups**, you typically plan for **pairwise equivalence testing**:

- Diclofenac vs. Piroxicam
- Diclofenac vs. PXM plus Counterirritant
- Piroxicam vs. PXM plus Counterirritant

This means you must **adjust α** to account for **multiple comparisons**, commonly using **Bonferroni correction**:

$$\text{Adjusted } \alpha = 0.05 / 3 = 0.0167 \rightarrow Z_{1-\alpha/2} \approx \mathbf{2.39}$$

Sample Size Formula and Calculation

Using the formula for equivalence trials:

$$n = ((Z_{1-\alpha/2} + Z_{1-\beta}) \times \sigma / \Delta)^2$$

Substituting the values:

$$n = ((2.39 + 0.84) \times 1.81 / 1.0)^2$$

$$n = (4.059 \times 1.81)^2 = (7.35)^2 = 54.0$$

Sample size per group (rounded): 54

Total sample size for 3 groups: 162

With 10% dropout:

Total = $162 / (1 - 0.10) \approx 180$ participants

Recommended: 60 participants per group

The clinical study will be recruited in total 180 subjects, which means 60 subjects per arm.

Justification:

- We used the reference from Kocak et al. because: The study used topical piroxicam, which is the main active ingredient in Counterpain PXM. The study was randomized, double-blind, and controlled, and reported the standard deviation of pain scores in full—a parameter that is essential for sample size calculations. To date, we have not found any publications comparing diclofenac gel directly with topical piroxicam, with standard deviations appropriate for use in statistical calculations. So, even though the comparator was capsaicin, this reference was chosen because it is quite representative in terms of pain type and study design.

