4. STUDY OBJECTIVES

The objectives of this study is to demonstrate the equivalency of efficacy and safety in reducing musculoskeletal pain between Piroxicam plus Counterirritant gel versus Piroxicam gel and Diclofenac gel, applied for 6 ± 1 days in Indonesian population.

Justification:

Piroxicam plus Counterirritant, Piroxicam, Diclofenac are considered as topical Non-Steroid Anti Inflammatory Drugs (NSAIDs). Diclofenac more common to use as a standard topical treatment since they have more clinical studies data than others topical NSAIDs. To demonstrate that Piroxicam plus Counterirritant has the same efficacy with Piroxicam, Diclofenac, the dedicated clinical study need to be conducted.

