7.4.2 Statistical Analysis Plan

The statistical analysis will be performed after data finalization and database lock, following the predefined analysis sets (PPS, FAS, and Safety Analysis Set). All analyses will be conducted using standard statistical software (e.g., SPSS, SAS, or R), with the level of statistical significance set at $p < 0.05$, unless otherwise adjusted.

Efficacy Analysis

- **Primary Endpoint (Pain Score using Brief Pain Inventory):**
 - **Test: Analysis of Covariance (ANCOVA)** adjusting for baseline BPI score

- **Equivalence testing:** Pairwise comparisons using **two one-sided t-tests (TOST)** to assess whether the difference in mean change from baseline falls within the equivalence margin (± 1.0)
- **Assumptions:** Normality and homogeneity of variance will be checked. If violated, non-parametric equivalent (e.g., **Wilcoxon rank-sum test**) will be used.
- **Secondary Endpoints:**
 - **Range of Motion (ROM) and Muscle Strength:**
 - **Test:** Repeated Measures ANOVA or mixed-effects model, depending on data completeness and correlation structure
 - If non-normal: **Friedman test** or **Wilcoxon signed-rank test** for within-group, **Kruskal-Wallis test** for between-group comparisons.
 - **Thermal Sensation, Comfort, and Acceptance (ASHRAE Scale):**
 - **Test:** Chi-square test or Fisher's exact test for categorical comparisons
 - **Ordinal regression** may be used to explore patterns of thermal perception across groups.
 - **Responding Analysis (pain reduction ≥ 3 points):**
 - **Test:** Chi-square test for group-wise comparison of response rates
 - **Risk difference** and **number needed to treat (NNT)** will be calculated.

Safety Analysis

- **Adverse Events (AEs) and Adverse Drug Reactions (ADRs):**
 - **Test:** Chi-square test or Fisher's exact test for comparing incidence across groups
 - Descriptive statistics for type, severity, onset, and duration
 - **Severity grading** and **causality assessment** using **Naranjo's algorithm**.
- **Rescue Medication Use:**
 - **Test:** Poisson regression or negative binomial regression if data are overdispersed
 - Summarized as a mean number of doses used per participant and compared between groups.

Demographic and Baseline Characteristics

- **Continuous Variables** (e.g., age, BMI):
 - **Test:** One-way ANOVA or **Kruskal-Wallis test** (if non-normal distribution)
- **Categorical Variables** (e.g., sex, diagnosis):
 - **Test:** Chi-square test or Fisher's exact test as appropriate

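### The 80% power in section 6.7 is for a single pair; if section 4 means equivalence to both comparators, 80% per pair gives only about 67% for that objective

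*Protocol*

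**What the plan says.** Section 4 sets one efficacy objective, equivalence "between Piroxicam plus Counterirritant gel versus Piroxicam gel and Diclofenac gel", and the justification beneath it repeats the aim: "To demonstrate that Piroxicam plus Counterirritant has the same efficacy with Piroxicam, Diclofenac".

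Section 6.7 says that with three groups "you typically plan for pairwise equivalence testing" and lists three pairs: diclofenac against piroxicam, and the test gel against each of them. It divides alpha by three ("Adjusted } \alpha = 0.05 / 3 = 0.0167"). Power is entered once, as "Power : 80% ($Z_{1-\beta} = 0.84", together with "Standard deviation (σ) : 1.81" and a margin of 1.0. The result is 54 per group, 162 in total, and 180 after 10% dropout.

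Section 7.4.2 analyses the primary endpoint by ANCOVA adjusted for baseline BPI and describes the equivalence step as "Pairwise comparisons using two one-sided t-tests (TOST) to assess whether the difference in mean change from baseline falls within the equivalence margin", with margin ±1.0. The general significance level is 0.05 unless otherwise adjusted. The TOST item gives no alpha of its own, and nothing says whether one, two or three pairs must succeed.

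**The concern.** Read plainly, section 4 is met when the test gel is shown equivalent to piroxicam gel and also to diclofenac gel. The chance that two tests both succeed is lower than the chance that either one does. Section 6.7 recognises that there are several comparisons, but it allows for this only on the false-positive side. Bonferroni protects claims made separately. A claim that needs every test to succeed requires no alpha correction (intersection-union principle), but it does lose power. On the both-required reading, the plan pays for a protection it does not need and leaves out the loss it does incur.

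What is at stake is how the sample size is understood. Someone who takes 80% as the chance of reaching the same-efficacy conclusion against both comparators would be relying on a figure that was never calculated for that conclusion.

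**Working it through.** **Inputs.** SD 1.81, margin ±1.0, alpha 0.05 or 0.0167, 54 evaluable and 60 recruited per arm with equal allocation (sections 6.7 and 7.4.2). Assumption: all true differences are 0. The protocol states none, and 0 is the favourable case for equivalence.

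**The plan's own figure.** The printed formula with its printed inputs gives ((2.39 + 0.84) × 1.81 / 1.0)² = (3.23 × 1.81)² = 34.2, so 35 per group. The printed 54 arises because the next line shows 4.059 in place of 3.23: (4.059 × 1.81)² = 53.98. The dropout step, 162 / 0.90 = 180, does reproduce. The 54 therefore does not come from a calculation that delivers 80% even for one pair at the adjusted alpha. That is a separate error, kept apart below.

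**Joint power when 80% per pair is granted.**
- Both test-gel differences contain the test-arm mean, so their correlation is (σ²/n) / (2σ²/n) = 0.5.
- At a true difference of 0, TOST power for a pair is 2Φ(c) − 1, with c = Δ/SE − z(1−α). Power of 80% means c = 1.2816.
- P(|Z₁| < c and |Z₂| < c) with correlation 0.5 is 66.6%. Independent tests would give 0.80² = 64%.
- For all three listed pairs, simulation gives 59.4%.

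This result does not depend on the SD, the margin or the sample size.

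**Power at the planned size.** With known SD and n = 54, SE = 1.81 × √(2/54) = 0.348 and Δ/SE = 2.871.
- One-sided 0.05: c = 2.871 − 1.645 = 1.226, giving 78.0% per pair.
- One-sided 0.0167: c = 2.871 − 2.128 = 0.743, giving 54.2% per pair.

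Simulation with a pooled estimated SD and t-based TOST gives slightly lower values:

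| Evaluable per arm | One-sided alpha | Per pair | Both test-gel pairs | All three pairs |
|---|---|---|---|---|
| 54 | 0.05 | 78% | 63% | 56% |
| 54 | 0.0167 | 53% | 31% | 26% |
| 60 (no dropout) | 0.05 | 83% | 71% | 65% |
| 60 (no dropout) | 0.0167 | 62% | 42% | 35% |

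The printed z of 2.39 corresponds to one-sided 0.00833. With it, the known-SD figures at 54 per arm fall to 36.7% per pair and 15.2% for both.

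**Separating the two causes at 0.0167 and 54 per arm.** From 80% to 53% (27 points) is the per-pair shortfall from the sample-size calculation. From 53% to 31% (22 points) is the joint requirement. At one-sided 0.05 nearly all of the gap, 78% to 63%, is the joint requirement.

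**Effect of baseline adjustment.** If 1.81 is an unadjusted SD, ANCOVA reduces it to 1.81 × √(1 − r²), where r is the baseline correlation. The protocol gives no r, so these values are assumptions:

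| Assumed r | Residual SD | Both pairs, 0.05 | Both pairs, 0.0167 |
|---|---|---|---|
| 0 | 1.81 | 63% | 31% |
| 0.3 | 1.73 | 70% | 41% |
| 0.5 | 1.57 | 83% | 60% |

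**The case against.** The strongest reply is that the both-required rule is inferred. It rests on the word joining the two comparators in section 4, which may simply list them. The operative statistical text leans the other way: section 6.7 plans three pairwise tests, one of which (diclofenac against piroxicam) the objective does not claim, and it applies Bonferroni, which fits separate claims. On that reading per-comparison power is the ordinary figure to quote. This stands, and the point is therefore conditional. It does not rescue the 80%, because at the adjusted alpha of 0.0167 and 54 per arm the per-comparison power is about 53%.

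A formal success rule could also sit in a separate SAP, and its absence here is not the finding. The finding is that this document prints a power that does not match its objective under the both-required reading, and that is not reached under the other.

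A reader might infer three stronger things that the documents do not support:
- That the protocol presents 80% as the power of the whole three-arm trial, or a split result as a risk of at most 20%. It says neither; 80% is listed as an input next to the text on pairwise testing.
- That the joint requirement alone brings power down to 31%. More than half of that fall is the separate per-pair shortfall.
- That joint power is certainly below 80%. This is so with SD 1.81 taken as the residual SD. If it is an unadjusted SD and the baseline correlation is near 0.5, the both-pairs figure at one-sided 0.05 is about 83%.

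**Conclusion.** The point holds in conditional form. Sections 4 and 6.7 are not aligned: the objective names two comparators, the power input covers one pair, and the alpha correction belongs to a different claim structure. If both test-gel comparisons must succeed, 80% per pair means about 67% for the objective, a loss of 13 points that would remain after the arithmetic in 6.7 is corrected. At the planned 54 evaluable per arm the both-pairs figure is about 63% at one-sided 0.05 and 31% at one-sided 0.0167.

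The 67% rests only on true differences of 0, equal arms and a shared test arm. The planned-size figures also need 1.81 to be the residual SD; with an assumed baseline correlation of 0.3 to 0.5 they become 70% to 83% and 41% to 60%. The trial can run as designed, but the printed power should not be relied on under either reading. This matters less than the sample-size arithmetic error in the same section.

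**What to change.** State the success rule and print the power that goes with it. Either version would be coherent:

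- **(a) Both required.** Section 7.4.2 says the objective is met only if both test-gel TOSTs succeed, each at one-sided 0.05 without Bonferroni. Diclofenac against piroxicam is labelled supportive. Section 6.7 prints the joint power at 54 evaluable per arm: about 63% with SD 1.81, with the ANCOVA range of 70% to 83% shown as resting on an assumed correlation of 0.3 to 0.5.
- **(b) Separate claims.** Section 4 is reworded so that each comparator is its own claim. Bonferroni is kept. Section 6.7 labels the power as per comparison and prints its recomputed value, about 53% at one-sided 0.0167 with SD 1.81, in place of 80%.

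Either costs a few sentences and no patients; the downside is a less favourable printed power. Restating the figure does not raise it. If the sponsor wants 80% for both pairs with SD 1.81, the known-SD calculation needs about 68 evaluable per arm at one-sided 0.05 (204 in total; 204 / 0.90, so 227 recruited), or about 90 at one-sided 0.0167 (270 in total; 300 recruited).

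### The sample-size calculation contains an addition error and omits the two-group factor: 54 evaluable per arm gives about 52% power per comparison at the adjusted one-sided level of 0.0167, not 80%

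*Protocol*

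**What the plan says.** Protocol section 6.7 assumes a pain-score SD of 1.81, a margin of 1.0, 80% power with a normal quantile of 0.84, and α = 0.05. It plans three pairwise equivalence comparisons, divides α by three to get 0.0167, and takes 2.39 as the two-sided critical value. The formula is "n = ((Z_{1-\alpha/2} + Z_{1-\beta}) \times \sigma / \Delta)^2", the substitution is "n = ((2.39 + 0.84) \times 1.81 / 1.0)^2", and the next line reads "n = (4.059 \times 1.81)^2 = (7.35)^2 = 54.0". The conclusion is "Sample size per group (rounded): 54", hence 162 in total and 180 after a 10% dropout allowance, or 60 enrolled per arm.

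Section 7.4.2 analyses the primary endpoint by pairwise two one-sided t-tests on mean change from baseline with margin ±1.0, "with the level of statistical significance set at $p < 0.05$, unless otherwise adjusted". Section 4 states the objective as equivalence of the test gel to both piroxicam gel and diclofenac gel.

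**The concern.** There are three separate faults.

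1. **The sum is wrong.** 2.39 + 0.84 is 3.23, not 4.059. This is not a text-extraction artefact, because 4.059 carries through to 7.35, 54, 162 and 180.
2. **The formula is a one-sample formula.** Each planned comparison is between two arm means, whose difference has variance 2σ²/n. The factor 2 is missing.
3. **The quantiles do not match the planned test.** In TOST with zero true difference, both one-sided tests must pass. The sample size then uses z(1−α) and z(1−β/2) = 1.28, not z(1−α/2) and z(1−β) = 0.84.

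The first fault raises the printed n; the second lowers it, and the third on balance lowers it too. They offset only in part. Section 5 describes the trial as confirmatory, and this calculation is its only justification for enrolling 180 people. If the power is much lower than stated, the trial could well fail to show equivalence between products that are in fact identical.

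**Working it through.** **Inputs.** SD 1.81, margin 1.0, 80% power, adjusted α 0.0167, 54 evaluable per arm and 10% dropout are from section 6.7. TOST with margin ±1.0 is from section 7.4.2. The protocol states no true difference; zero is assumed, which is the most favourable case.

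**The plan's own figure**

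- As printed: (4.059 × 1.81)² = 7.35² ≈ 54.0. The 54 follows from 4.059 alone.
- With the sum done correctly: (3.23 × 1.81)² = 5.846² = 34.2, or 35 per arm.
- The dropout step is right: 162 / 0.90 = 180.

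**Repairing the formula**

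- Factor 2 added, protocol quantiles kept: 2 × [(2.394 + 0.8416) × 1.81]² = 68.6, or 69 per arm.
- TOST form, n per arm = 2[(z(1−α) + z(1−β/2))σ/Δ]²:
  - one-sided 0.0167: 2 × [(2.128 + 1.2816) × 1.81]² = 76.2, or 77 (78 with the t distribution)
  - one-sided 0.0083, the level that 2.39 implies per test: 88.5, or 89 (90 with t)
  - one-sided 0.05: 56.1, or 57 (57 with t)

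Of the variants tried (with and without the factor 2; one-sided 0.05, 0.025, 0.0167 and 0.0083; both power quantiles), only one comes near 54. It is a two-sample superiority formula at unadjusted two-sided 0.05, which gives 52. That is neither the adjusted level nor the planned test.

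**Power with 54 evaluable per arm.** The standard error of a difference is 1.81 × √(2/54) = 0.348, so margin/SE = 2.871. The normal approximation is 2Φ(2.871 − z(1−α)) − 1. At 0.0167 this is 2Φ(0.743) − 1 = 54.2%. Exact t-based values integrate over the distribution of the sample variance:

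| One-sided α per test | Normal approximation | Exact TOST power per comparison |
|---|---|---|
| 0.0083 (z = 2.39) | 36.7% | 33.9% |
| 0.0167 | 54.2% | 52.4% |
| 0.05 | 78.0% | 77.3% |

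**Joint power, by simulation with a shared test arm.** Equivalence to both comparators: about 31% at 0.0167 and 63% at 0.05. All three pairs listed in section 6.7: about 25% at 0.0167.

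**Size for 80% per comparison at 0.0167.** 78 evaluable per arm; 78 / 0.90 = 86.7, so 87 enrolled per arm and 261 in total.

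**The case against.** The addition error and the missing factor cannot be defended. What can be argued is how far the headline power figure should be trusted.

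- **The level is open to reading.** Section 6.7 adjusts to 0.0167 but then takes a two-sided quantile, which is 0.0083 per side; section 7.4.2 defaults to 0.05. Taking 0.0167 as the level of each one-sided test is the natural TOST reading, but it is a reading. This stands, and is why all three levels are shown. None gives 80%.
- **The 31% joint figure may penalise twice.** If equivalence to both comparators is required, no α split is needed and 63% is the matching figure. If α is split, each comparison can be claimed separately and the 52% matters. This is fair. The 31% describes the plan only if section 4 is read as requiring both while the split in section 6.7 is kept.
- **Failure is not always the likelier outcome.** At 0.0167, success on any one comparison is slightly more likely than not. Success against both at 0.05 is about 63%. Failure is the likelier outcome for the two-comparator objective at the adjusted level (about 69%), but not at 0.05.
- **ANCOVA could help.** If 1.81 is an SD before baseline adjustment, assumed baseline correlations of 0.3, 0.5 and 0.6 would give about 62%, 76% and 86% at 0.0167 (normal approximation). The protocol states no correlation and takes no credit for one, so this does not rescue its calculation.
- **All 60 might be evaluable.** Power would then be 61.5% at 0.0167 and 82.7% at 0.05. But the primary analysis set is per protocol, and the plan itself budgets for a 10% loss.

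In the other direction, a true difference of 0.25 lowers the 52% to about 42%.

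**Conclusion.** The concern holds. The figure of 54 rests on a wrong sum in a formula that suits neither a two-arm comparison nor TOST. At the protocol's adjusted α used one-sided, 54 evaluable per arm gives 52% power per comparison, almost 28 percentage points below the stated 80%. At the most lenient level in the document, 0.05, it gives 77%. For equivalence to both comparators the figures are about 31% and 63%.

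These figures assume that 1.81 is the SD of the analysed quantity, that the true difference is zero, and that no precision is gained from baseline adjustment. The arithmetic error depends on none of these assumptions. The power claim must be corrected before the sample size can be regarded as justified.

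**What to change.** In section 6.7:

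1. Delete 4.059 and the line built on it.
2. Replace the formula with n per arm = 2[(z(1−α) + z(1−β/2))σ/Δ]², and state the assumed true difference.
3. Fix one significance level for the one-sided tests, with the matching success rule, and use it in both section 6.7 and section 7.4.2.
4. Restate the power that 54 evaluable per arm delivers at that level: about 52% per comparison and 31% for both at 0.0167, or 77% and 63% at 0.05.
5. If credit is to be taken for ANCOVA, state the assumed baseline correlation and its source.

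If the claim is to require equivalence to both comparators, each comparison can be tested at one-sided 0.05 without a split. That recovers most of the per-comparison shortfall at the present size, although joint power remains about 63%. If the 0.0167 split and 80% per comparison are both to be kept, 78 evaluable per arm are needed, about 261 enrolled.

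Correcting the statement costs protocol wording only and no additional patients. The price is a less favourable stated power.

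### The 80% power in section 6.7 is not tied to the quantity tested in section 7.4.2: the type of the pain-score SD of 1.81 is unstated, and the equivalence test may be on raw or ANCOVA-adjusted change

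*Protocol*

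**What the plan says.** Protocol section 6.7 lists "Outcome : Pain score", "Standard deviation (σ) : 1.81" and "Clinically meaningful margin (Δ or δ) : 1.0", with 80% power and alpha 0.05 divided by three for the pairwise comparisons. The SD comes from a randomised trial of topical piroxicam against topical capsaicin, chosen partly because it "reported the standard deviation of pain scores in full". The visit is not given, nor whether the SD is of a score or of a change. No baseline-to-follow-up correlation appears. The result is 54 evaluable per arm, raised to 60 for 10% dropout.

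Protocol section 7.4.2 gives two entries for the primary pain endpoint. One is ANCOVA "adjusting for baseline BPI score". The other is pairwise TOST "to assess whether the difference in mean change from baseline falls within the equivalence margin" of ±1.0. The section does not say whether the TOST uses the ANCOVA estimate or a plain comparison of mean changes.

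**The concern.** A score at one visit, a change from baseline and a baseline-adjusted difference generally have different SDs, and the required sample size goes with the square of the SD. Section 6.7 commits to an SD, a power and a sample size, and section 7.4.2 commits to a test, but nothing connects them. The reader cannot tell whether 1.81 is too large, too small or right for the test that will be run. Equivalence is the trial's objective. If power for the tested quantity is well below 80%, a failure to show equivalence says little, and the protocol as written does not let anyone judge that risk.

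**Working it through.** **The plan's own figure.** With the printed inputs, 2.39 + 0.84 = 3.23, and (3.23 × 1.81 / 1.0)² = 34.2, so 35 per arm. The next printed line uses 4.059 in place of 3.23, with no source, and (4.059 × 1.81)² = 54.0. The formula also lacks the factor 2 for comparing two arms (2 × 34.2 = 68.4, so 69), and it is not a TOST formula. The TOST form for 80% power at a true difference of 0 is n = 2 × ((z(1−α) + z(0.90)) × SD / margin)²:

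- one-sided 0.0167: 2 × ((2.128 + 1.282) × 1.81)² = 76.2, so 77 per arm;
- one-sided 0.05: 2 × ((1.645 + 1.282) × 1.81)² = 56.1, so 57 per arm.

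The dropout step, 162 / 0.90 = 180, is correct.

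**Power at SD 1.81, before any question of score or change.** Power = 2Φ(1.0/SE − z(1−α)) − 1, with SE = SD × √(2/54). At SD 1.81, SE = 0.348 and 1/SE = 2.871. Power is 2Φ(0.743) − 1 = 54% at one-sided 0.0167, and 78% at one-sided 0.05. This is the reference against which an SD effect should be read.

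**Effect of the quantity tested.** Assumptions that are not in the protocol: 1.81 is the SD at both baseline and final visit, the true difference is 0, and the correlation rho runs from 0.3 to 0.7. Then:

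- SD of raw change = 1.81 × √(2(1 − rho));
- residual SD under ANCOVA = 1.81 × √(1 − rho²).

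Results for one comparison with 54 per arm (normal approximation):

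| Quantity in the TOST | rho | SD | Power, one-sided 0.0167 | Power, one-sided 0.05 | n per arm for 80% at 0.0167 |
|---|---|---|---|---|---|
| Raw change | 0.3 | 2.14 | 23% | 57% | 107 |
| Raw change | 0.5 | 1.81 | 54% | 78% | 77 |
| Raw change | 0.7 | 1.40 | 89% | 96% | 46 |
| ANCOVA-adjusted | 0.3 | 1.73 | 62% | 83% | 70 |
| ANCOVA-adjusted | 0.5 | 1.57 | 77% | 91% | 58 |
| ANCOVA-adjusted | 0.7 | 1.29 | 94% | 98% | 39 |

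Allowing for the t distribution lowers the 0.0167 figures by about one or two percentage points.

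**Reading the table.** Raw change matches SD 1.81 exactly at rho 0.5, loses power below that and gains above it. The ANCOVA SD is never above 1.81. The ratio of the ANCOVA SD to the raw-change SD is √((1 + rho)/2), which is below 1 for every rho below 1, so under equal variances the adjusted test is the more powerful. At rho 0.3 the choice between the two moves power from 23% to 62%.

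**The case against.** The strongest reply is that the planned analysis already answers most of this. Section 7.4.2 names ANCOVA for this endpoint. With baseline as covariate, the treatment difference is the same whether the response is the final score or the change, and the residual SD cannot exceed the SD of the response. If 1.81 is a final-visit SD, it is conservative. Which estimate feeds the TOST could be left to a statistical analysis plan, which is not at hand.

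Much of that stands. It does not close the point, because the power claim is in the protocol, 6.7 mentions neither change nor adjustment, and the TOST is a separate entry described as t-tests on mean change.

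Three stronger inferences are tempting and should not be drawn:

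- **That 1.81 is the wrong SD.** The protocol calls it an SD of pain scores but never gives its visit or type. The documents show only that its nature is unstated.
- **That the SD explains a fall from 80% to 54%.** At rho 0.5 the raw-change SD is exactly 1.81, so the SD contributes nothing there. That gap belongs to the formula and arithmetic in 6.7.
- **That a low correlation is likely because diagnoses are mixed and no minimum baseline pain is required.** The protocol gives no figure, and an unrestricted baseline range tends to raise a correlation, not lower it.

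**Conclusion.** The point holds as a missing link between the power statement and the test. It does not show that the SD is wrong. Taking 1.81 as the SD at each visit, a true difference of 0, 54 per arm and one-sided 0.0167, power runs from about 23% to 89% for raw change and from about 62% to 94% for the adjusted difference as rho goes from 0.3 to 0.7. The reference at SD 1.81 is 54%, not 80%. Relative to that reference, the direction of the SD effect is unknown for raw change and only favourable under ANCOVA. The equal-variance assumption and the range of rho are mine; neither is in the protocol.

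**What to change.** - **Section 7.4.2:** run each pairwise TOST on the baseline-adjusted (ANCOVA) difference. Compare its 90% confidence interval with ±1.0, or use the multiplicity-adjusted equivalent (100% − 2 × 1.67% = 96.7% if the one-sided level is 0.0167).
- **Section 6.7:** say which SD 1.81 is. If it is a final-visit SD, use it as a conservative SD for the adjusted difference. If it is a baseline SD, state the equal-variance assumption needed to use it.
- **Section 6.7:** restate the power of 54 evaluable per arm for that same quantity with a correct two-sample TOST formula, and show a range over rho such as 0.3 to 0.7.

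The correction costs a few lines and needs no extra patients or data. The adjusted test uses data already collected and, under equal variances, is more powerful than raw change at every rho below 1. The downside is that the restated power may be less favourable than 80%, and the sponsor would then have to decide whether the planned size is still acceptable.
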